13.2 Compliance Calculation

Compliance will be separately analyzed for the PA and LTE analysis, in the same manner as exposure was analyzed.

PA: 52-week treatment period

For the 52-week treatment period, compliance with treatment is defined as the number of tablets taken during a period divided by the number of tablets that should have been taken during that period, multiplied by 100 to yield a percentage, i.e.:

$$\text{Compliance with treatment} = 100 \times \left(\frac{N_1}{5 \times N_2} \right)$$

where

- N_1 = number of tablets given minus number of tablets returned over N_2 days,
- N_2 = number of days between treatment start and treatment termination visit,

where N_1 will be computed using the BATCH form of the eCRF and N_2 corresponds to the exposure time expressed in days (see Section 13.1 for exposure time and number of tablets ingested formulas).

For the 52-week treatment period, the last kit dispensed is at Week 48 visit. The number of tablets returned for this last kit is entered during Week 52 visit.

Example: Let's consider the example from Section 13.1. The subject has been provided with 510 tablets, returned 34 tablets and has been exposed to study drug for 90 days. Therefore, N_1 is

equal to $510 - 34 = 476$ and N_2 is equal to 90, which gives a compliance equal to $100 * (476 / 5*90) = 105.8\%$.

For subjects with missing number of tablets returned (e.g. lost to follow-up), the compliance will be calculated by imputing the missing returned amount with the number of tablets the subjects should have returned if 100% compliance was observed while on treatment for the associated dispensed kit.

Compliance with treatment will be tabulated by treatment group from first intake to last intake of 52-week treatment period.

Compliance with treatment will also be presented into categories as follows:

- $< 60\%$
- $\geq 60\%$ to $< 80\%$
- $\geq 80\%$ to $\leq 100\%$
- $> 100\%$ to $\leq 110\%$
- $> 110\%$

LTE analysis: LTE period

Compliance for the LTE period will be presented on subjects from LTE SAF.

For the LTE period, compliance with treatment is defined using the formula below (4 tablets taken per day, 2 in the morning and 2 in the afternoon):

$$\text{Compliance with treatment} = 100 \times \left(\frac{N_1}{4 \times N_2} \right)$$

The compliance will be computed using the number of kits dispensed as well as the number of tablets returned. Compliance with treatment will be tabulated by treatment group from first intake in LTE to last intake during LTE period and also presented within categories, as for the 52-week treatment period.

The first kit dispensed in LTE treatment period is at Week 52 visit for subjects who rolled over directly from 52-week treatment to LTE.

LTE analysis: Overall period (i.e. 52-week treatment period + LTE)

Overall compliance will be presented on LTE SAF only on subjects who received evobrutinib 50 mg BID during the 52-week treatment period and continue with the same dose of evobrutinib during LTE period.

Overall compliance with treatment is defined using the formula below:

$$\text{Compliance with treatment} = 100 \times \left[\left(\frac{N_1}{5 \times N_2} \right) + \left(\frac{N_3}{4 \times N_4} \right) \right] / 2$$

where

- N_1 = number of tablets given minus number of tablets returned over N_2 days for the 52-week treatment period
- N_2 = number of days between treatment start and treatment termination visit for the 52-week treatment period
- N_3 = number of tablets given minus number of tablets returned over N_2 days for the LTE treatment period
- N_4 = number of days between treatment start and treatment termination visit for the LTE treatment period

Compliance with treatment will be tabulated from first intake to last intake of the study and also presented within categories, as for the 52-week treatment period.

Subject data listings:

For each analysis, the following listings will be provided:

- listing of kit numbers with date of dispense, and number of tablets returned (from BATCH).
- listing of start/end dates with number ingested tablets (from EXPOSUREDT).
- listing with exposure time, cumulative dose, and compliance.

14 Endpoint Evaluation

For all efficacy endpoints:

- Analysis visits will be used (as detailed in Section 9.7 and Appendix 18.11).
- Baseline definition from Section 9.5 should be applied.
- Statistical tests of the two-primary and key secondary efficacy endpoints entering the hierarchical testing procedure (see section 14.1.2.4) will be conducted at a one-sided α level of 0.025. The one-sided p-values and the two-sided 95% CIs will be presented as well as a note on how to interpret correctly the two-sided 95% CIs by considering appropriately the accurate boundary of the interval.

For ALL other endpoints, statistical tests will be conducted at two-sided α level of 0.05, and two-sided p-values and 95% CI will be presented where applicable.

14.1 Two-primary Efficacy Endpoints

The two-primary efficacy endpoints will be analyzed for the PA using mITT Analysis Set.

14.1.1 Definitions

The two-primary efficacy endpoints are SRI response at Week 52:

- SRI-4 response in all subjects,
- SRI-6 response in the HDA subgroup.

The SRI-4 response, a measure of reduced SLE disease activity, is defined by meeting all of the following conditions compared to Baseline:

1. ≥ 4 -point reduction in SLEDAI-2K total score.
2. No significant worsening in PGA score (< 0.3 increase assuming the PGA score is on a 0-3 scale).
3. No new BILAG A organ domain scores and ≤ 1 new BILAG B organ domain score compared to Day 1 using BILAG 2004.
4. No institution of EAC-determined protocol-prohibited medication/treatment (i.e., EAC-treatment failure)

Subjects with missing values at Week 52 after the implementation of rules defined in Appendices 18.1.1 and 18.1.3 will be considered as non-responder in the primary analysis.

Assessment of criterion #4 will be confirmed by an Endpoint Adjudication Committee (EAC). Further details can be found in the EAC Charter.

The SRI-6 response is defined similarly to SRI-4, based on a ≥ 6 -point reduction in SLEDAI-2K total score.

Details of derivation are described in Appendix 18.1.

14.1.2 Primary Analysis of the Two-primary Endpoints

Table 17 outlines all planned statistical analyses of the two-primary endpoints. In the context of estimands, handling the intercurrent events is also explained in the table.

Table 17 : Analysis of the two-primary endpoints

Analysis	Analysis Population	Analysis Method	Data Handling Notes and handling of intercurrent events
Two Primary endpoints / MCP	mITT Analysis Set	
 Presentation of adjusted Odds-Ratio (OR), 2-sided 95% CI of OR, nominal 1-sided p-value, adjusted 1-sided p-value ($\alpha=0.025$) from Logistic Regression Number and percentage of responders in each dose group, observed Δ in response proportions from Placebo for each dose group 	
A subject with a missing response at Week 52 will be considered a non-responder at Week 52.
 
Subjects with endpoint adjudication committee (EAC)-determined treatment failure based on protocol-prohibited medication will be considered as non-responder.
 
(Estimand: composite strategy)

Sensitivity 1 (Per Protocol Analysis)	PP Analysis Set	
 • Presentation of OR, 2-sided 95% CI of OR, nominal p-value from Logistic Regression • Number and percentage of responders in each dose group, observed Δ in response proportions from Placebo for each dose group 	Same as Primary Analysis
Sensitivity 2 (Multiple Imputation Analysis)	mITT Analysis Set	
 • Presentation of OR, 2-sided 95% CI of OR, nominal p-value from Logistic Regression • Number and percentage of responders in each dose group, observed Δ in response proportions from Placebo for each dose group 	
For subjects with missing response at Week 52, the multiple imputation (MI) will be used to impute the missing data using the available observations.
 
Subjects with endpoint adjudication committee (EAC)-determined treatment failure based on protocol-prohibited medication will be considered as non-responder.
 
(Estimand: composite strategy)

Sensitivity 3 (Tipping Point Analysis)	mITT Analysis Set	
 • Presentation of study conclusion at each possible combinations of responders from each treatment group. 	
Tipping Point Analysis
 
Subjects with endpoint adjudication committee (EAC)-determined treatment failure based on protocol-prohibited medication will be considered as non-responder.
 
(Estimand: composite strategy)

Sensitivity 4 (Unadjusted Analysis)	mITT Analysis Set	
 • Presentation of unadjusted OR, 2-sided 95% CI of OR, nominal p-value from Logistic Regression • Number and percentage of responders in each dose group, observed Δ in response proportions from Placebo for each dose group 	Same as Primary Analysis
Sensitivity 5 (Background therapy Adjusted Analysis)	mITT Analysis Set	
 • Presentation of adjusted OR, 2-sided 95% CI of OR, nominal p-value from Logistic Regression. The logistic model will include the background therapy of immunosuppressant use as covariate 	Same as Primary Analysis
Supportive 1 (Trend test for Dose Response)	mITT Analysis Set	Test of linear trend in log odds of response with increasing dose, based on an appropriate contrast from the logistic model, ie, (3, 1, -1, -3).	Same as Primary Analysis

MCP = Multiplicity Control Procedure. See section 14.1.2.4 for details.

Treatment failures are determined by EAC based on their review of protocol-prohibited medications. Further details can be found in the EAC Charter.

14.1.2.1 Primary Analysis Method of SRI-4 and SRI-6

The null and alternative hypotheses corresponding to the two-primary endpoints are:

$$H_{0a}: \log(\text{OR}_{4_all}) \leq 0 \text{ versus } H_{1a}: \log(\text{OR}_{4_all}) > 0$$

$$H_{0b}: \log(\text{OR}_{6_HDA}) \leq 0 \text{ versus } H_{1b}: \log(\text{OR}_{6_HDA}) > 0$$

where $\log(\text{OR}_{4_all})$ and $\log(\text{OR}_{6_HDA})$ are the log of odds ratio for SRI-4 in all subjects and SRI-6 in the HDA subjects.

The study will be declared positive if the treatment effect is significant in at least one of the primary endpoints. The global hypothesis testing problem is stated as:

$$H_0: H_{0a} \cap H_{0b}$$

$$H_1: H_{1a} \cup H_{1b}.$$

The global null hypothesis is rejected if one or both individual null hypotheses are rejected.

To account for the multiplicity due to the two-primary endpoints and multiple treatment comparisons with placebo for each primary endpoint, the multiple testing procedure as described in Section 14.1.2.4 will be performed.

In the primary analysis of the two-primary endpoints, a subject could be considered as an SRI-4 or SRI-6 Non-Responder if the subject takes EAC-determined protocol-prohibited medications during the treatment period (i.e., EAC-treatment failure). The EAC will make the final determination on whether the subject should be classified as treatment failure. In addition, a subject with a missing response at Week 52 will be considered a non-responder at Week 52.

The primary analysis of the SRI-4 response at Week 52 among all subjects, and SRI-6 response at Week 52 among HDA subjects, will be based on the mITT analysis set, and analyzed using logistic regression model for the odds of a given SRI response adjusted for the stratification variables used in the randomization (race: black vs non-black, screening SLEDAI-2K total score: <10 vs ≥ 10 and region: US and Western Europe vs Japan vs ROW) and with treatment as a factor. The estimated OR, together with associated two-sided 95% CI of the estimated OR, nominal one-sided p-value and adjusted one-sided p-value ($\alpha=0.025$) from the logistic regression model, comparing each evobrutinib treatment group to placebo will be presented.

If there is model convergence problem due to for example zero cells in covariates, appropriate method will be applied to resolve the issue.

An example of SAS code is available in Appendix 18.9.

In addition, the number and percentage of SRI-4/SRI-6 non-responders at Week 52 in each treatment group will be presented as follows:

- For the summary of SRI responders (Yes), the number and percentage of subjects from each treatment group who have met the responder criterion for each SRI component will be provided, including the delta from placebo.
- For the summary of SRI non-responders (No), the number and percentage of subjects from each treatment group who are imputed as non-responders for each reason will be provided. Reasons of non-response will be as follows:
 - Missing scoring at Week 52
 - Treatment discontinuation due to Safety (reasons = AEs, death)
 - Treatment discontinuation due to Lack of efficacy
 - Other treatment discontinuation (reasons = lost to follow-up, protocol non-compliance, withdrew consent and others)
 - Treatment completer and missing response at W52

In addition, a bar chart will be generated by treatment group to present SRI-4 through SRI-10 response rates at Week 52. The same figure will be repeated on HDA subgroup. A line plot representing the SRI response rate over time will be also provided for each primary endpoint, with all treatment groups on the same graph. The figure presenting data over time will use the similar imputation rules as applied for the Week 52 timepoint.

SRI-4/SRI-6 response rates over time will be also presented by visit, using similar imputation rules as applied for the Week 52 timepoint.

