8.2.2 Analysis Sets

Table 3 provides the definitions of the Analysis Sets and their purposes.

[figure not shown]
The analysis sets for PA will be drawn from all subjects randomized as of November 28, 2018 (n = 469), see Sections 6.2 and 7. Subjects not randomized (screen failure) will be included in PA analysis set if their screening date is on or before November 28, 2018. For the LTE analysis, the analysis sets will be drawn from all subjects who enter the LTE.

For analysis on HDA subpopulation, all subjects with SLEDAI-2K ≥ 10 at Screening will be included. The corresponding analysis sets will be drawn as specified above depending on the analysis (PA, LTE analysis).

Table 3: Analysis Sets

Analysis Set	Definition	Purpose
Enrolled	The Enrolled analysis set will include all subjects who sign the informed consent form.	The purpose of this analysis set is to count how many subjects signed the informed consent

ITT (Intent-To-Treat) Analysis Set	The ITT analysis set will include all randomized subjects. Subjects will be analyzed according to randomization treatment.	The ITT will be used for demographic/baseline characteristics.
mITT (modified Intent-To-Treat) Analysis Set	The mITT analysis set will include all randomized subjects who have received at least one dose of IMP (evobrutinib or placebo) and have at least one Baseline and one post-Baseline disease assessment (among the following: SFI, SLEDAI-2K, PGA, BILAG 2004, CLASI). Subjects will be analyzed according to randomized treatment. Subjects with Protocol Deviation (PD) code equal to PDEV80 are excluded from mITT.	The mITT will be used for all efficacy endpoints. The mITT will be used for demographic/baseline characteristics in case more than 10% of ITT are excluded from mITT.
Safety Analysis Set (SAF)	The Safety analysis set will include all subjects who have received at least one dose of IMP (evobrutinib or placebo). Subjects will be analyzed according to the actual treatment they receive.	The SAF will be used for the analysis of medications, exposure/compliance and safety endpoints.

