8.2.3 Subgroup Analysis

Table 4 below defines the subgroups to be used for subgroup analysis as described in Section 14 and Section 15.

Subgroup analysis on the stratification factors race (Black versus non-Black) and, disease activity prior to dosing on Day 1 (SLEDAI-2K total score < 10 versus ≥ 10 at Screening) will be defined using the eCRF data. The stratification factor region (US and Western Europe, Japan, and RoW) will be defined using Interactive Web Response System (IWRS) as only collected as part of randomization data.

Table 4: Subgroups and Strata

Subgroup	Content	Definition
A	Disease Activity at Screening (HDA) (stratification factor)	non-HDA: SLEDAI-2K total score < 10; HDA: SLEDAI-2K total score ≥ 10 (from SLEDAI1 form of the eCRF) Some analysis will be presented on HDA subpopulation (i.e. including all HDA subjects) as detailed in Sections 14 and 15.
B	Serological Activity status at Screening	Positive: positive anti-dsDNA (i.e. > 15 U/mL) OR complement levels (C3 or C4 below (<) LLN); Negative: otherwise, i.e. negative/indeterminate anti-dsDNA and C3/C4 complement levels above or equal (>=) LLN (from Central Laboratory: anti-dsDNA, serum C3 and serum C4)
C	Race (stratification factor)	Black or African American; other (from DEM form of the eCRF)
D	Region (stratification factor)	US and Western Europe; Japan; ROW (from IWRS)
E	Ethnicity 1	Hispanic/Latino VS Non-Hispanic/Latino (from DEM form of the eCRF)
F	Background Therapy of Immunosuppressant	Yes; No (derived from Concomitant Medication form of eCRF, using the L04A ATC code, see Section 14.1.2.2 for derivation detail)
IWRS = Interactive Web-Response System		

CCI [REDACTED]

Table 5: Exploratory Subgroups and Strata

Subgroup	Content	Definition
CCI	[Redacted]	[Redacted]
CCI	[Redacted]	[Redacted]

9 General Specifications for Data Analyses

All statistical analyses will be performed by PPD Inc., except the modeling and simulation analysis and the gene expression, which will be performed by Merck/EMD Serono or delegate.

CCI

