9.3 Data handling for the planned analyses

For the PA, data will be handled according to the corresponding Data Handling Report and Interim Database Lock Plan.

The stratification factors race (Black versus non-Black) and disease activity prior to dosing on Day 1 (SLEDAI-2K total score < 10 versus ≥ 10 at Screening) will be summarized using both the eCRF data and the IWRS data in demographics and baseline characteristics. However, for statistical analyses, eCRF data will be used. The stratification factor region (US and Western Europe, Japan, and RoW) will be defined using IWRS. (See Section 8.2.3, Table 4)

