Parameter of the SLEDAI-2K score (Screening)	
From SLEDAI1 form of the eCRF:
 
 • Central nervous system 
 ○ Cardiovascular accident (CVA)/Cranial nerve disorder/Lupus headache/Organic brain syndrome/Psychosis/Seizure/Visual disturbance • Musculoskeletal 
 ○ Arthritis/Myositis • Renal 
 ○ Hematuria/Proteinuria/Pyuria/Urinary casts • Skin 
 ○ Alopecia/Mucosal ulcers/Rash • Cardio-pulmonary 
 ○ Pericarditis/Pleurisy • Hematologic 
 ○ Leukopenia/Thrombocytopenia • Serologic 
 ○ Increase DNA binding/Low complement • Vascular 
 ○ Vasculitis • Constitutional 
 ○ Fever
Total SLEDAI-2K score (Screening)	
 • SLEDAI-2K < 10, SLEDAI-2K ≥ 10 (HDA subgroup [Yes/No]) from SLEDAI1 form of the eCRF • SLEDAI-2K < 10, SLEDAI-2K ≥ 10 (HDA subgroup [Yes/No]) from IWRS 
Note: Total SLEDAI-2K score and Clinical Total SLEDAI-2K score (excluding the components ‘Increase DNA Binding’ and ‘Low Complement’) at Screening will also be presented.

HDA Subject	
 • Yes/No (derived with Total SLEDAI-2K score at Screening from eCRF and from IWRS)

Table 15: Other Baseline Characteristics

Other Baseline Characteristic	Modality
SLICC/ACR damage	From SLICC form of the eCRF:

index score	
 • 0 • 1 • ≥ 2 and < 5 • ≥ 5
BILAG Severity	
From BILAG form of the eCRF:
 
 • Severe = At least 1 BILAG A; vs. • Moderate = At least 2 BILAG B and no BILAG A; vs. • Mild = 1 BILAG B and no BILAG A and no more than 1 BILAG B. • No severity = Criteria for severe, moderate and mild not met
CLASI total activity score	
From CLASI form of the eCRF:
 
 • < 8 • ≥ 8 • Summary statistics for LTE analysis
SFI Flare	
From SFI1 form of the eCRF:
 
 • No flares, • Mild or moderate flare, • Severe flare, • Missing

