18.9.1 SRI Response

Logistic regression: PROC LOGISTIC with SAS

The logistic regression can be implemented using the following SAS code:

```
proc logistic data=<dataset> descending;
  class TreatmentGroup(ref='Placebo') Region Race SLEDAI_2K_screening;
  model AVALC(event="Y") = TreatmentGroup Region Race
                        SLEDAI_2K_screening / orpvalue clodds=wald;
  ods output CLoddsWald=CLoddsWald;
run;
```

For primary analysis of the 2-primary endpoints and key secondary endpoint *SRI-4 response at Week 52 among serologically active subgroup*, output the 1-sided p-value ($\alpha=0.025$) as below:

- When the OR favors the active treatment (i.e. $OR > 1$), one-sided p-value = two-sided p-value / 2
- When the OR does not favor the active treatment (i.e. $OR \leq 1$), one-sided p-value = 1 – (two-sided p-value / 2)

The interaction can be implemented using the “*” symbol. For example, the following statement takes into consideration the interaction between treatment and region:

```
proc logistic data=<dataset> descending;
  class TreatmentGroup(ref='Placebo') Region Race SLEDAI_2K_screening;
  model AVALC(event="Y") = TreatmentGroup Region Race SLEDAI_2K_screening
                        TreatmentGroup * Region / orpvalue clodds=wald;
  ods output ParameterEstimates=ParameterEstimates CLoddsWald=CLoddsWald;
run;
```

Linear trend in log odds of SRI response for two-primary and key secondary endpoints: PROC LOGISTIC with SAS

In addition to the standard logistic model, the linear trend test can be implemented using the ESTIMATE and CONTRAST statements:

```
proc logistic data=<dataset>;
  class TreatmentGroup Region Race SLEDAI_2K_screening / param=glm;
  model AVALC(event="Y") = TreatmentGroup Region Race
                        SLEDAI_2K_screening;
  ESTIMATE "SRI response rate trend linear in treatment" TreatmentGroup 3 1 -1 -
3;
  CONTRAST "SRI response rate trend linear in treatment" TreatmentGroup 3 1 -1 -3
/ e;
  ods output
  Estimates=Estimates ContrastTest=ContrastTest;
run;
```

Logistic regression subgroup analysis: PROC GLIMMIX with SAS

In addition to the standard logistic model, the subgroup analysis can be implemented using the following code:

```
proc glimmix data=<dataset>;
  class TreatmentGroup (ref='Placebo') SLEDAI_2K_screening;
  model AVALC(event="Y") = TreatmentGroup SLEDAI_2K_screening TreatmentGroup*
  SLEDAI_2K_screening / alpha=0.05 dist=binary;

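### In the SRI-6 model for HDA subjects the screening SLEDAI-2K <10 vs ≥10 covariate is constant, so the model reduces to treatment, race and region and leaves the spread of scores unused

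*SAP*

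**What the plan says.** Section 14.1.2.1 describes one logistic regression for both primary endpoints. Its subject is "The primary analysis of the SRI-4 response at Week 52 among all subjects, and SRI-6 response at Week 52 among HDA subjects", and the model is "adjusted for the stratification variables used in the randomization (race: black vs non-black, screening SLEDAI-2K total score" and region). The disease-activity and region terms are written as "screening SLEDAI-2K total score: <10 vs ≥ 10 and region", and treatment enters as a factor.

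The HDA population is fixed in Section 8.2.2: "For analysis on HDA subpopulation, all subjects with SLEDAI-2K ≥ 10 at Screening will be included". Table 4 in Section 8.2.3 takes this classification "from SLEDAI1 form of the eCRF". Section 9.3 says that race and the SLEDAI-2K stratum are summarised from both the eCRF and the IWRS, and then: "However, for statistical analyses, eCRF data will be used".

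The sample code in Section 18.9.1 keeps the stratum as a classification variable, "class TreatmentGroup(ref='Placebo') Region Race SLEDAI_2K_screening", and has no separate version for HDA subjects. The same list recurs for:

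- Sensitivity Analysis #5 for SRI-6 (Section 14.1.2.2);
- SRI-6 with sustained OCS reduction in HDA subjects (Table 19, which refers back to the primary method);
- the HDA and non-HDA repeats in Sections 14.2.2.3 and 14.3.1.1.

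The continuous score is available. Table 14 in Section 11.2.1 summarises "Total SLEDAI-2K score and Clinical Total SLEDAI-2K score" at Screening, and the change from Baseline in the total score is itself the first SRI component.

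**The concern.** The variable that selects the HDA subjects and the covariate meant to adjust for disease activity are one variable with one cut. A reader of Section 14.1.2.1 would think that the SRI-6 model carries three adjustment terms; it carries two. Choosing the eCRF rather than the IWRS value as covariate closes the only route by which the term could have varied.

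SRI-6 is a fall of at least 6 points on the same score. HDA subjects can start at 10 or well above it, and the model uses none of that spread. The SAP does otherwise elsewhere: in Section 14.3.4 the SF-36 and FACIT-Fatigue responder models adjust for the baseline value as well as the strata.

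Precision matters here for two reasons. SRI-6 in HDA is one of two primary tests, in about half the sample. It is also a gate: under Section 14.1.2.4, testing goes on to the key secondary endpoints and lower doses only if both primary null hypotheses are rejected for the highest dose.

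**Working it through.** **1. Is the term constant?** HDA means eCRF screening SLEDAI-2K ≥10 (Sections 8.2.2 and 8.2.3). The covariate is eCRF screening SLEDAI-2K, <10 vs ≥10 (Sections 9.3 and 14.1.2.1). Every HDA subject therefore has the value ≥10. In a simulated HDA data set of 206 subjects in four arms:

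- without the term: 1 intercept + 3 treatment + 1 race + 2 region = 7 columns, rank 7;
- with the term: 8 columns, rank still 7.

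The three treatment log-odds ratios were identical in the two fits, and their standard errors agreed to five decimals. In the HDA and non-HDA repeats the term is constant in each half.

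**2. The plan's own power.** Inputs from Section 8.2.1: 103 evaluable per arm, 50% HDA (51.5 per arm), one-sided 0.0125 per endpoint, SRI-4 40% vs 60%, SRI-6 30% vs 55% (or 50%). With z = 2.2414,

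power = Φ[(Δ − z·s0)/s1], s0 = √(2p̄(1−p̄)/n), s1 = √((p1(1−p1)+p2(1−p2))/n).

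- SRI-4: (0.20 − 2.2414×0.0697)/0.0683 = 0.64, giving 74.0%.
- SRI-6, +25 points: (0.25 − 2.2414×0.0974)/0.0943 = 0.34, giving 63.2%.
- SRI-6, +20 points: (0.20 − 2.2414×0.0965)/0.0945 = −0.17, giving 43.1%.

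Power for at least one endpoint is P4 + P6 − P(both). The correlation between the two statistics is not stated. At 0.7 the result is 80.5% and 76.3%, which matches the stated 80% and 76%. These figures rest on an unadjusted chi-squared test, so the inert covariate does not alter them.

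**3. What a continuous score could add.** The SAP does not say how strongly the score predicts SRI-6 within HDA, so this is an assumed range. Trials were simulated with 52 per arm and 30% vs 55%, and logistic models were fitted with and without the continuous covariate. Repeated runs of 3,000 to 8,000 trials per setting agreed within simulation error. At one-sided 0.0125:

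| Assumed latent correlation | Unadjusted power | Gain from the covariate |
|---|---|---|
| 0 | about 63% | about 0 points |
| 0.1 | about 63% | about 1 point |
| 0.2 | about 63% | about 2 points |
| 0.3 | about 63% | 3 to 4 points |
| 0.5 | about 63% | 8 to 9 points |

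On a log-odds scale per SD of score, power without and with the covariate was 63% and 63% (0), 62% and 64% (0.25), 65% and 67% (0.5), 62% and 68% (0.75), and 62% and 71% (1.0).

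At 0.025, the level that the larger of the two p-values must meet for Hochberg to reject both hypotheses, power rises from about 75% to 77% at correlation 0.3 and to 79–81% at 0.5.

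**4. Effect on study success.** With SRI-4 power at 74.0% and correlation 0.7 between the test statistics, raising SRI-6 power from 63% to 66% moves power for at least one endpoint from 80.5% to 81.4%. Raising it to 72% gives 83.4%.

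**The case against.** The strongest reply is that nothing in the result is wrong. Restriction to HDA already conditions fully on the SLEDAI-2K stratum. Section 14.1.2.1 promises adjustment for the randomisation strata, and within HDA that promise is kept. This stands. A reader might infer that the SRI-6 test is biased or invalid, or that the SAP promises adjustment for continuous severity and fails to deliver it. The documents support neither reading.

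A reader might also infer that the plan forfeits about 9 points of power. That is the upper end of an assumed range that includes zero. The score is already truncated at 10. SRI-6 also depends on PGA, BILAG, adjudicated treatment failure and missing data counted as non-response, all of which can dilute its link with the starting score.

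Three further points stand. About 52 per arm is the design figure; the cohort of 469 in Section 8.2.2 would give about 469/4 × 0.5 ≈ 59 HDA subjects per arm before mITT exclusions. A continuous covariate also changes the conditional odds ratio being estimated. And version 4.0 was written after review of the primary results, so a changed model cannot now be prespecified for them.

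The general clause in Section 14.1.2.1 on convergence problems does not settle the matter: it names neither this term nor a method.

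**Conclusion.** The point holds as one of model specification and precision. In every HDA-only model that uses the Section 14.1.2.1 list, the <10 vs ≥10 term does nothing, and the SAP neither drops nor replaces it. Bias, type I error and the stated power are unaffected.

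The cost is roughly 0 to 9 points of marginal SRI-6 power at one-sided 0.0125, for about 52 per arm, 30% vs 55%, and an assumed latent correlation of 0 to 0.5. On the inputs in step 4, the gain in power for at least one endpoint is about 1 to 3 points for correlations of 0.3 to 0.5. The SRI-4 model in all subjects is not affected, because there the term varies.

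**What to change.** State that the <10 vs ≥10 term drops out of HDA-only models. For SRI-6 in HDA, specify in its place the continuous Baseline SLEDAI-2K total score as defined in Section 9.6:

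logit(SRI-6) = treatment + race + region + Baseline SLEDAI-2K.

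Baseline rather than Screening is the value to name, because the two can differ and SRI-6 is measured from Baseline. Leave the SRI-4 model as it is.

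For the primary results already reviewed, report this model as a labelled supplementary analysis, and describe the primary SRI-6 model as adjusted for race and region within the HDA stratum.

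The cost is a short SAP statement and one further model call. The downsides are an assumption of linearity on the logit scale and a slightly different conditional odds ratio from the current model. If the score turns out not to be prognostic, the simulations show essentially no loss of power.
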